5.3.2 Antibiotics

Prophylactic antibiotics or anti-virals are not required on this trial.

5.3.3 Hydration

No pre-hydration or hydration is required with this regimen.

5.3.4 Tumor lysis prevention and management

Participants with bulky disease and/or circulating disease $\geq 15,000$ circulating malignant cells/ mm³ may receive allopurinol 300mg orally daily for 7-10 days starting with the first dose of Imprime PGG and rituximab. Participants deemed at risk for tumor lysis syndrome (TLS) should have their labs monitored per standard practice. The management of established TLs should also follow standard practice.

CONFIDENTIAL

This document is confidential. Do not disclose or use except as authorized.

5.3.5 Other

Blood product transfusions and the use of bisphosphonates are permitted at the discretion of the treating physician.

5.4 Duration of Therapy

Duration of therapy will be for four weeks but will be stopped in the event of any of the following:

- Intercurrent illness that prevents further administration of treatment
- Unacceptable adverse event(s)
- Participant demonstrates inability or unwillingness to comply with the medication regimen and/or documentation requirements
- Participant decides to withdraw from the study
- General or specific changes in the participant's condition render the participant unacceptable for further treatment in the opinion of the treating investigator

5.5 Duration of Follow-up

Participants who have received at least one dose of Imprime PGG and Rituximab will be followed for 1 year after the completion of combination therapy or until death, whichever comes first.. Participants removed from the study for unacceptable adverse events will be followed until resolution or stabilization of the adverse event. The post-treatment visit (Section 9) will occur 10 weeks +/- 3 days from the last day of treatment.

5.6 Criteria for Removal from Study Treatment

Participants will be removed from study when any of the criteria listed in Section 5.4 applies. The reason for study removal and the date the participant was removed must be documented in the study-specific case report form (CRF). Alternative care options will be discussed with the participant.

In the event of unusual or life-threatening complications, participating investigators must immediately notify the Principal Investigator, [name]. at [contact].

6. EXPECTED TOXICITIES AND DOSING DELAYS/DOSE MODIFICATIONS

Dose delays and modification will be made using the recommendations in Section 6.3. Toxicity assessments will be done using the Version 4.0 of the NCI Common Terminology Criteria for Adverse Events (CTCAE) which is identified and located on the

CONFIDENTIAL

This document is confidential. Do not disclose or use except as authorized.

CTEP website at:

http://ctep.cancer.gov/protocolDevelopment/electronic_applications/ctc.htm.

If possible, symptoms should be managed symptomatically. In the case of toxicity, appropriate medical treatment should be used (including anti-emetics, anti-diarrheals, etc).

All adverse events experienced by participants will be collected from the time of the first dose of the study treatment, through the study and until the final study visit. Participants continuing to experience toxicity at the off study visit may be contacted for additional assessments until the toxicity has resolved or is deemed irreversible.

6.1 Anticipated Toxicities from Imprime PGG

A list of the adverse events and potential risks associated with Imprime PGG appear below and will determine whether dose delays and modifications will be made or whether the event requires expedited reporting **in addition** to routine reporting.

- Less likely toxicities (5-20%)
 - Increase in Aspartate Aminotransferase (AST) and Alkaline phosphate (ALK) levels in the blood
 - Skin rash or dry skin
 - Diarrhea
 - Electrolyte disturbances: decrease in potassium, magnesium, and/or phosphate levels in the blood
 - Hair loss
 - Anemia
 - Decreased appetite
 - Increase in amylase levels in the blood
 - Headache
 - Allergic reaction
 - Hypertension
 - Dyspnea
 - Conjunctivitis
 - Increased or decreased number of white blood cells
 - Mouth sores
 - Nausea or vomiting
 - Swelling around finger nails
 - Arthralgia
 - Fever

CONFIDENTIAL

This document is confidential. Do not disclose or use except as authorized.

- Rare but serious toxicities (<5%)
 - Dehydration
 - Fluid around the lungs
 - Blood clot that travels to the lungs
 - Death (refer to Section 2.1.1.3)

6.2 Anticipated Toxicities from Rituximab

A list of the adverse events and potential risks associated with rituximab appear below and will determine whether dose delays and modifications will be made or whether the event requires expedited reporting **in addition** to routine reporting.

- Infusion reactions: including fever, chills, headache, nausea, vomiting, throat irritation, flushing, rash, pruritis, urticaria, dyspnea, increased cough, rhinitis, asthenia, and hypotension, primarily during rituximab infusions which typically respond to an interruption of the infusion and resumption at a slower rate.
 - Fatal Infusion Reactions: Severe and fatal cardiopulmonary events, including angioedema, hypoxia, pulmonary infiltrates, acute respiratory distress syndrome, myocardial infarction, and cardiogenic shock, have been reported. These severe reactions typically occurred during the first infusion with time to onset of 30-120 minutes.
- Night sweats
- Abominal pain, pain, back pain
- Sinusitis
- Diarrhea
- Myalgia
- Arthralgia
- Hypertension
- Dizziness
- Anxiety
- Tumor Lysis Syndrome: tumor lysis syndrome has been reported and is characterized in patients with a high number of circulating malignant cells ($\geq 25,000$ ul) by rapid reduction in tumor volume, renal insufficiency, hyperkalemia, hypocalcemia, hyperuricemia, and hyperphosphatemia.
- Mucocutaneous Reactions: Severe bullous skin reactions, including fatal cases of toxic epidermal necrolysis and paraneoplastic pemphigus, have been reported. The onset of reaction has varied from 1 to 13 weeks following rituximab exposure.
- Metabolic Events: Hyperglycemia, peripheral edema, LDH increase
- Hematologic Events: including lymphopenia, neutropenia, leukopenia, thrombocytopenia with a median duration of approximately 14 days. Transient aplastic anemia (pure red cell aplasia) and hemolytic anemia have been reported.

CONFIDENTIAL

This document is confidential. Do not disclose or use except as authorized.

- Late onset neutropenia, marrow hypoplasia, and prolonged pancytopenia have also been reported.
- **Infectious Events:** B cell depletion and decreased serum immunoglobulins have been associated with an increased risk of bacterial and viral infections. Serious infections (grade 3 or 4) are rare, occurring in approximately 2% of patients.
 - **Hepatitis B Reactivation:** Hepatitis B virus (HBV) reactivation with fulminant hepatitis, hepatic failure, and death has been reported in some patients with hematologic malignancies treated with rituximab. The majority of patients received rituximab in combination with chemotherapy. The median time to the diagnosis of hepatitis was approximately four months after the initiation of rituximab and approximately one month after the last dose.
 - **Other Serious Viral Infections:** including JC virus (progressive multifocal leukoencephalopathy [PML]), cytomegalovirus, herpes simplex virus, parvovirus B19, varicella zoster virus, West Nile virus, and hepatitis C. In some cases, the viral infections occurred up to one year following discontinuation of Rituximab and have resulted in death.
 - **Progressive multifocal leukoencephalopathy (PML):** PML is a rare and demyelinating disease of the brain caused by infection with the JC virus that usually leads to death or severe disability. JC virus infection resulting in PML and death has been reported rarely in patients with hematologic malignancies receiving rituximab. The majority of these patients had received rituximab in combination with chemotherapy or as part of a hematopoietic stem cell transplant.
 - The following serious adverse events have been reported to occur in patients following completion of rituximab infusions: arthritis, disorders of blood vessels (vasculitis, serum sickness and lupus-like syndrome), eye disorders (uveitis and optic neuritis), lung disorders including pleuritis and scarring of the lung (bronchiolitis obliterans), that may result in fatal outcomes, and fatal cardiac failure.

6.3 Toxicity Management

Toxicity management should follow standard clinical practice. Specific recommendations that apply to both Imprime PGG and rituximab follow:

6.3.1 Infusion toxicity

Infusion should be temporarily discontinued for a temperature > 101.3F, mucosal edema, or >30 mm Hg decrease in systolic blood pressure. Hypersensitivity reactions should be treated per DFCI institutional guidelines (See Appendix A). If hypersensitivity occurs, an additional 25 mg of diphenhydramine IV should be given. Participants with hypersensitivity should also receive methylprednisolone 50 mg IVB and ranitidine 50 mg IVB. Participant with bronchospasm should be

CONFIDENTIAL

This document is confidential. Do not disclose or use except as authorized.

treated with supplemental oxygen and nebulizers as needed. Infusion may resume after symptoms resolve at 50% of the rate infusing at the time of the event.

Participants with life threatening infusional reactions including cardiac arrhythmia, pulmonary infiltrates, acute respiratory distress syndrome, myocardial infarction, cardiogenic shock, or anaphylactoid events should not be re-challenged and should be removed from study. No dose reductions will be made for infusional reactions. Section 6.4 outlines the protocol for dose delays in the setting of an infusion reaction to either agent.

6.3.2 Hematologic toxicities

The only hematologic parameter that must be met on each treatment day is an ANC ≥ 1000 . Hematologic toxicities should be managed by standard use of transfusions and growth factors. In particular, white blood cell growth factor use (e.g., neupogen) is acceptable on this study. A dose delay of up to 1 week for recovery of neutropenia to an ANC ≥ 1000 is acceptable on this study.

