5.2 Rituximab administration

Rituximab from a commercial supply will be administered IV at a dose of 375 mg/m² every 7 days for 4 weeks. Actual body weight will be measured prior to each Rituximab infusion to calculate the BSA and dose for each infusion.. If the infusion cannot be completed within 1 day, the patient is allowed to receive the remainder of the infusion the following day as long as the dose is administered within 2 consecutive days.

Rituximab will be administered at DFCI per Dana-Farber Harvard Cancer Center institutional guidelines.

Dana-Farber Harvard Cancer Center institutional guidelines include:

CONFIDENTIAL

This document is confidential. Do not disclose or use except as authorized.

Imprime PGG and rituximab for relapsed indolent NHL

November 13, 2018

- Participants will be pre-medicated with hydrocortisone 100 mg IV, acetaminophen 650 mg, and diphenhydramine 25 mg PO, or their equivalents, prior to each dose.
- No specific prehydration is required.
- The first infusion will begin at an initial rate of 50 mg/hour for the first hour. If hypersensitivity or infusion-related events do not occur, the rate will be increased in 50 mg/hour increments every 30 minutes until a maximal rate of 400 mg/hour.
- On subsequent infusions the initial rate in the absence of hypersensitivity will be 20 percent of the total dose over 30 minutes, followed by the remaining 80 percent of the total dose over 60 minutes.
- Vital signs should be checked approximately every 15 minutes during the first hour of infusion, then approximately once an hour or prior to any infusion rate change until completion of the infusion.
- Infusion should be temporarily discontinued for a temperature > 101.3°F, mucosal edema, or >30 mm Hg decrease in systolic blood pressure.
- An additional 25 mg of benadryl IV should be given.
- Infusion may resume after symptoms resolve a 50% of the rate infusing at the time of the event.

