6.4 Dose Modifications/Delays

No dose reductions will be made. Participants unable to tolerate the specified dose of either Imprime PGG or rituximab will be removed from study. Imprime PGG and/or rituximab infusion should be interrupted for severe reactions, e.g., rapid tumor lysis. Treatment of infusion-related symptoms with diphenhydramine and acetaminophen is recommended. Additional treatment with bronchodilators or IV saline may be indicated. Epinephrine, antihistamines, and corticosteroids should be available for immediate use in the event of a hypersensitivity reaction to rituximab (e.g., anaphylaxis). In most cases, the infusion can be resumed at a 50% reduction in rate from the last known rate (e.g., from 100mg/hr to 50mg/hr) when symptoms and laboratory abnormalities have completely resolved. Infusions should be discontinued in the event of serious or life-threatening cardiac arrhythmias. Subjects who develop clinically significant arrhythmias should undergo cardiac monitoring during and after subsequent infusions. Whether to discontinue the infusion and when to restart the infusion of either agent following a non-life threatening infusion reaction is up to the discretion of the treating physician. In the event of a non-life threatening infusion reaction to Imprime PGG, patients must be rechallenged within one week, and rituximab may be delayed by up to 24 hours following the successful infusion of Imprime PGG. In the event of a non-life threatening infusion

CONFIDENTIAL

This document is confidential. Do not disclose or use except as authorized.

reaction to rituximab, dosing of Imprime PGG and rituximab may be delayed by up to one week.

A temporary delay of all study dosing may occur if the subject's health precludes study drug administration (i.e., subject is experiencing an adverse event that requires hospitalization; ANC <750.) Subjects that require permanent discontinuation of rituximab, or fail to receive any rituximab for ≥ 7 consecutive days from the missed dose, or ≥ 14 consecutive days in total, should discontinue all study drug administration.

Participants will be removed from study when any of the criteria listed in Section 5.4 apply. The reason for study removal and the date the participant was removed must be documented in the study-specific case report form (CRF). Alternative care options will be discussed with the participant.

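### Section 6.4 gives a different ANC figure for delaying dosing from the one 6.3.2 requires to treat, and on one unexcluded count of days a permitted one-week delay also meets the 6.4 rule for stopping study drug

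*Combined protocol and SAP*

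**What the plan says.** **ANC needed to treat.** Section 6.3.2: "The only hematologic parameter that must be met on each treatment day is an ANC ≥ 1000". Footnote 2 of the Section 9 study calendar carries the requirement to all treatment days, but as strictly greater than 1000.

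**ANC as a ground for delay.** Section 6.4: "A temporary delay of all study dosing may occur if the subject's health precludes study drug administration". After an 'i.e.' it gives two conditions: "subject is experiencing an adverse event that requires hospitalization; ANC <750".

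**Permitted delays.** Section 6.3.2 calls acceptable "A dose delay of up to 1 week for recovery of neutropenia to an ANC" of at least 1000. After a non-life-threatening infusion reaction to rituximab, Section 6.4 says "dosing of Imprime PGG and rituximab may be delayed by up to one week".

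**Stopping rule.** Section 6.4 calls for an end to all study drug in subjects who "fail to receive any rituximab for ≥ 7 consecutive days from the missed dose, or ≥ 14 consecutive days in total".

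**Schedule.** Both drugs are given every 7 days for four doses (Sections 5.1 and 5.2), on days 1, 8, 15 and 22. Section 9 allows a window of 3 days either side unless otherwise noted. Section 5.2 adds: "If the infusion cannot be completed within 1 day, the patient is allowed to receive the remainder of the infusion the following day". Neither 5.2 nor 6.4 says whether a partly infused dose is a missed one.

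**The concern.** These are rules for holding and stopping study drug, and a site should reach the same decision from whichever section it opens.

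On ANC, 6.3.2 and 6.4 give different figures for the same decision. A patient at 750 to 999 cannot be treated under 6.3.2 or footnote 2, yet does not meet the neutrophil condition that 6.4 lists for a delay.

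On delay, the longest hold that 6.3.2 accepts is one week, and the shortest gap that triggers the 6.4 stop is 7 days. Dosing is weekly, so holding a dose to the next weekly slot lands exactly on that boundary. Two sites could then handle the same patient differently, one giving the remaining doses and the other stopping all study drug, only because they count days differently.

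**Working it through.** The plan gives no calculated figure on this point, so there is none to reproduce. The check compares the thresholds and counts days.

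**ANC.** Inputs: at least 1000 to treat (6.3.2), more than 1000 to treat (Section 9, footnote 2), below 750 as a ground for delay (6.4).

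| ANC | 6.3.2 allows treatment | Footnote 2 allows treatment | 6.4 delay condition met |
|---|---|---|---|
| 749 | no | no | yes |
| 750 to 999 | no | no | no |
| 1000 | yes | no | no |
| 1001 | yes | yes | no |

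The mismatch between 6.4 and the other two covers 750 to 999. The difference between 6.3.2 and footnote 2 affects only a value of exactly 1000.

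**Days.** Take a dose due on day 8, with the previous dose given on time on day 1 and no rituximab given on day 8. Compare a 6-day delay (given day 14) with a 7-day delay (given day 15).

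| Count | 6-day delay | 7-day delay | Limit | Met at 7-day delay? |
|---|---|---|---|---|
| Elapsed from scheduled date | 14 − 8 = 6 | 15 − 8 = 7 | 7 | yes |
| Rituximab-free days, scheduled day included | days 8–13 = 6 | days 8–14 = 7 | 7 | yes |
| Rituximab-free days, scheduled day excluded | days 9–13 = 5 | days 9–14 = 6 | 7 | no |
| From end of +3-day window (day 11) | 14 − 11 = 3 | 15 − 11 = 4 | 7 | no |
| Elapsed since last dose | 14 − 1 = 13 | 15 − 1 = 14 | 14 | yes |
| Rituximab-free days since last dose | days 2–13 = 12 | days 2–14 = 13 | 14 | no |

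The counts are the same for doses due on days 15 and 22. With the previous dose on time, a delay of 6 days or less meets neither limb on any of these counts. That condition matters for the 14-day limb. Suppose the dose due on day 8 was given on day 5, inside the window. If the next dose stays scheduled for day 15, a 4-day delay (given day 19) is already 19 − 5 = 14 elapsed days.

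The 14-day limb is a separate test. On elapsed time since the last dose it is met at a 7-day delay, however the 7-day limb is counted.

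**Doses at stake.** For an overlap at week 2, 3 or 4, the doses not yet given are 4 − 1 = 3, 4 − 2 = 2 and 4 − 3 = 1. This assumes that a delayed course is still completed, which the documents do not state.

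**Rituximab reaction.** The one-week delay that 6.4 allows here reaches the same 7-day boundary, but only if the delayed dose counts as missed.

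**The case against.** The strongest reply is that the sections can be read together. Section 6.3.2 is the specific rule for neutropenia and speaks of a delay, not a missed dose. On that view a dose given within the permitted week is delayed, and only a dose still not given after it is missed. Excluding the missed-dose day, or starting after the window, also removes the overlap on the 7-day limb. This stands as an available reading, and it is why the point is conditional. But Section 6.4 does not say that a permitted delay is not a missed dose, and it does not say which count applies. A site that counts from the scheduled date is not misreading it.

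On ANC, the reply is that nothing conflicts in practice: 6.3.2 is mandatory, 6.4 is permissive, and 6.3.2 supplies its own authority to delay. That stands, and it makes this the lesser point. The 750 cannot be set aside as the entry criterion of Section 3.1.5, because 6.4 applies it to dosing on study and footnote 2 separates eligibility from the treatment-day limit.

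A reader might infer more than the documents support:

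- **That 6.4 allows dosing at 750 to 999.** It does not; it only lists when a delay may occur.
- **That the stopping rule has no starting point at all.** The 7-day limb does name the missed dose. What is missing is the calendar date this means. Only the 14-day limb has no stated start.
- **That reactions to Imprime PGG create a general conflict.** Section 6.4 says "patients must be rechallenged within one week, and rituximab may be delayed by up to 24 hours following the successful infusion of Imprime PGG", which allows up to 7 + 1 = 8 days. A gap of 7 or 8 days arises only near the latest permitted timing, and only if no rituximab was given on the original day. The point does not rest on this route.

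**Conclusion.** The inconsistency is real, limited in extent and worth correcting. The ANC figures differ over 750 to 999, and 6.3.2 still governs there. The more important part is the delay. If a delayed dose counts as missed and days run from its scheduled date, a dose held for the full week is both permitted by 6.3.2 and a reason to stop under 6.4. The 14-day limb gives 14 or 13 days for the same delay, according to whether elapsed or rituximab-free days are counted. With the previous dose on time, the overlap is confined to the 7-day delay.

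At stake are the remaining planned doses of a patient who reaches that boundary. The documents give no expected frequency, so the number of patients affected cannot be estimated. A reader might go on to infer that the response-rate analysis is compromised; nothing in the documents ties these rules to evaluability, and no such effect is claimed.

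**What to change.** Amend Sections 6.3.2, 6.4 and 9 (including footnote 2) together so that:

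- the ANC conditions for treating and for delaying agree;
- no permitted delay, including the one after a rituximab reaction, also meets the discontinuation rule;
- the date from which the 7 days and the 14 days are each counted is stated, as is whether elapsed or rituximab-free days are meant;
- the text says whether the 3-day window applies to these counts;
- the text says whether a delayed dose, or one partly infused under Section 5.2, counts as missed.

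The clinical team chooses the values; none is proposed here. The cost is one clarifying amendment, with no added procedures or patients.

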6.3.3 Non-hematologic toxicities

In the case of asymptomatic laboratory abnormalities (e.g., LFT abnormalities), no intervention is required. Symptomatic abnormalities should be managed using standard clinical guidelines.

6.4 Dose Modifications/Delays

No dose reductions will be made. Participants unable to tolerate the specified dose of either Imprime PGG or rituximab will be removed from study. Imprime PGG and/or rituximab infusion should be interrupted for severe reactions, e.g., rapid tumor lysis. Treatment of infusion-related symptoms with diphenhydramine and acetaminophen is recommended. Additional treatment with bronchodilators or IV saline may be indicated. Epinephrine, antihistamines, and corticosteroids should be available for immediate use in the event of a hypersensitivity reaction to rituximab (e.g., anaphylaxis). In most cases, the infusion can be resumed at a 50% reduction in rate from the last known rate (e.g., from 100mg/hr to 50mg/hr) when symptoms and laboratory abnormalities have completely resolved. Infusions should be discontinued in the event of serious or life-threatening cardiac arrhythmias. Subjects who develop clinically significant arrhythmias should undergo cardiac monitoring during and after subsequent infusions. Whether to discontinue the infusion and when to restart the infusion of either agent following a non-life threatening infusion reaction is up to the discretion of the treating physician. In the event of a non-life threatening infusion reaction to Imprime PGG, patients must be rechallenged within one week, and rituximab may be delayed by up to 24 hours following the successful infusion of Imprime PGG. In the event of a non-life threatening infusion

CONFIDENTIAL

This document is confidential. Do not disclose or use except as authorized.

reaction to rituximab, dosing of Imprime PGG and rituximab may be delayed by up to one week.

A temporary delay of all study dosing may occur if the subject's health precludes study drug administration (i.e., subject is experiencing an adverse event that requires hospitalization; ANC <750.) Subjects that require permanent discontinuation of rituximab, or fail to receive any rituximab for ≥ 7 consecutive days from the missed dose, or ≥ 14 consecutive days in total, should discontinue all study drug administration.

Participants will be removed from study when any of the criteria listed in Section 5.4 apply. The reason for study removal and the date the participant was removed must be documented in the study-specific case report form (CRF). Alternative care options will be discussed with the participant.

